### 2.2.3. Hypotheses

We expect that an app running on participants' own smartphones is a feasible way of remotely monitoring mood symptoms during pregnancy. We do not have any hypotheses regarding the difference in adherence to sampling protocols, timeliness of data collection and data completeness between the *retrospective* and the *retrospective plus momentary assessments* strategies.

## 3. Methods

### 3.1. Study Design

We will use a parallel, randomised control trial (RCT) study design. For the study assessing the use of tablet computers in antenatal clinics, participants will be randomly assigned to complete (i) an app version of the Whooley questions and the EPDS in which the questionnaires are presented using a scrolling layout (i.e., App screening – Scrolling), or (ii) an app version of the Whooley questions and the EPDS in which the questionnaires are presented using a paging layout (i.e., App screening – Paging).

Participants will also be asked if they wish to take part in the study evaluating an app through a BYOD approach. Those consenting to take part in this study will be randomly assigned to (i) complete the EPDS once a month for 6 months (i.e., retrospective assessment), or to (ii) complete the EPDS, plus 4 days of EMA of mood, sleep, worry, enjoyment and energy, plus EPDS once a month for 6 months (i.e., retrospective plus momentary assessment).

In selected sites, we will recruit an additional 30 participants into the app through a BYOD approach study. Participants recruited from these sites will receive feedback on their data from designated members of the clinical team.

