A systematic review has also been conducted concerning conceptions and measures of engagement across the field of computer science, which included 351 studies (under review). Along with the identification of 102 unique definitions of engagement, this review showed that work on engagement has largely been driven by situated experiments, by Flow Theory, by forward-looking developmental work and by gaming and learning applications. This review therefore highlighted the need for longitudinal and ecologically valid studies of user engagement with technology. A second narrative review of the theory behind, applications of, and design lessons to be garnered from previous implementations of systems for ecological momentary assessment was also conducted; the insights from which are applied in the development of the application at the centre of this study. Related work has focused on the differences between momentary and retrospective forms of self report from both the user's perspective and with respect to the objective analysis of data collected by such means (under review).

The aim of the current study is twofold: (1) assessing the feasibility of using tablet computers for implementing the recommendations of the *Antenatal and postnatal mental health: clinical management and service guidance* NICE guideline for recognising depression in pregnancy in the waiting area of antenatal clinics in general practices, midwifery services or secondary care sites; and (2) assessing the feasibility of using an app for the repeated and longitudinal assessment of depressive symptoms and mood-related factors (through EMA techniques) during pregnancy using a bring-your-own-device (BYOD) approach. Additionally, it will explore the feasibility of having a member of the clinical care team providing regular feedback to patients on their data.

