## 2.2. App through a BYOD approach

The aim of this study is to determine the feasibility of using an app running on participants' own devices (i.e., through a BYOD approach) for the monitoring of depressive symptoms and mood-related constructs during pregnancy. We will assess the overall response rates of potential participants who are approached and asked to take part in this study. We will also compare two monitoring strategies, *retrospective* (using the EPDS) versus *retrospective plus momentary* (EPDS complemented with the EMA of mood, sleep, enjoyment, energy and worry), in terms of (1) drop-out rates, (2) adherence to sampling protocols, (3) patterns of engagement, (4) acceptance to participants, (5) timeliness of data collection, and (6) data completeness. We will assess if the implementation of a EMA technique affects the EPDS scores of participants allocated to the *retrospective plus momentary* condition. Additionally, we will assess if feedback by a member of the clinical care team affects engagement with the app, and participants' and clinicians' perceived usefulness of this approach.

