### 2.2.2. Secondary Objectives

- To assess differences in drop-out rates between the participants allocated to the retrospective assessment strategy (i.e., EPDS), and those allocated to the retrospective plus momentary assessment strategy (i.e., EPDS complemented with the EMA of mood, sleep, energy, enjoyment and worry).
- To assess differences in participants' adherence to sampling protocols between a retrospective assessment strategy (i.e., EPDS), and a retrospective plus momentary assessment strategy (i.e., EPDS complemented with the EMA of mood, sleep, energy, enjoyment and worry). We will achieve this by comparing the proportion of participants in each group that complete 100% of the expected assessments.
- To assess differences in usage patterns of the app between a retrospective assessment strategy and a retrospective plus momentary assessment strategy, including additional voluntary self-reporting, time spent using the app, number of interactions with other sections of the app, time to complete the self-assessments, and other ancillary usage data
- To assess differences in participants' acceptance of the app between a retrospective assessment strategy and a retrospective plus momentary assessment strategy through a post-study self-administered questionnaire

- To assess differences in timeliness of data collection between a retrospective assessment strategy and a retrospective plus momentary assessment strategy. We will achieve this by comparing the proportion of participants completing their assessments in response to a prompt displayed on their mobile devices between the two groups
- To assess differences in data completeness between a retrospective assessment strategy and a retrospective plus momentary assessment strategy. We will achieve this by comparing the proportion of complete records between the two groups
- To evaluate the impact of a momentary assessment technique of the EPDS scores by comparing the EPDS scores obtained at the start of the sampling period and the EPDS scores obtained at the end of this period. This will be assessed in the *retrospective plus momentary assessment* condition only
- To assess if feedback provided by a healthcare practitioner influences participants' and clinicians' engagement, acceptance and perceived usefulness of an app used for the remote and longitudinal monitoring of mood symptoms throughout pregnancy

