#### 3.5.2.2.4. Feedback by a human supporter

Sites choosing to take part in this part of the study, will identify a member of the clinical care team who will be in charge of reviewing participants' data, and of providing feedback to them through a desktop web interface that will be developed by [name] (they will not be using an app on their personal devices for this purpose). The type of feedback that participants will receive will be through templates that the designated member of staff will tailor to each participant. The most appropriate content for these templates will be identified through the co-design sessions outlined in *Section 3.5.1.2*. The designated member of the clinical care team **will not** replace the person conducting the procedures outlined in *Section 3.5.2.2.2. Duty of care*. In addition, the provision of feedback to participants **is not** intended to be an emergency or out-of-hours service. No personal contact details will be exchanged between participants and the designated member of the clinical team.

The designated members of the clinical team will be required to spend no more than 30 minutes once a week reviewing participants' data and providing feedback. After the study, they will be asked to take part in semi-structured interviews to assess their general sense of usefulness of this method and to complete a post-study survey (Appendix 7).

For participants in this experimental condition, we will assess their sense of connectedness and general sense of usefulness through additional questions in the post-study acceptance survey (Appendix 4).

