#### 3.6. Sample size

According to Matthey (2004), the minimal clinically significant difference for the EPDS (calculated using a reliable change index (RCI) and a standard deviation of 4) is 4 points. Therefore, for the study using tablet computers in antenatal clinics, in order to demonstrate a one-sided equivalence between the two layouts (i.e., scrolling versus paging) of the EPDS using an additive model (i.e., the mean score difference between the two groups not exceeding 3 points) with an alpha level of 0.025, power of 0.80 and a standard deviation of 4 we would need 126 participants. In addition, in order to demonstrate the PPV, PNV and FOR of the Whooley questions we would need at least 30 events (i.e., women scoring 10 points or higher on the EPDS). Assuming a prevalence of depression in pregnant women of 12%, we would need to recruit 250 participants. For these reason, we will aim to recruit a total sample of at least 300 participants.

For the app through a BYOD approach study, we aim to determine adherence to sampling protocols. We have chosen to relate the proposed sample size to the 95% confidence interval for the rate, as recommended by the Research Design Service in London. Therefore, we would need 96 participants in each arm with a 95% confidence level and a confidence interval of 10. This translates into a total sample of 192 (i.e., 96 participants in each experimental group). For this reason, we will aim to recruit at least 200 participants.

For the additional condition where participants will receive feedback from a designated member of the clinical care team, we aim to recruit 30 participants.

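### The plan asks whether clinician feedback changes engagement, but feedback is not randomised, is offered only at sites that opt in, and has no described same-site comparison group

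*Combined protocol and SAP*

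**What the plan says.** Two places word this part as a question about an effect. The objective in section 2.2.2 is "To assess if feedback provided by a healthcare practitioner influences" the engagement, acceptance and perceived usefulness reported by participants and clinicians. The aim in section 2.2 is that "we will assess if feedback by a member of the clinical care team affects engagement with the app", together with perceived usefulness. The last paragraph of section 1 also speaks of an impact on engagement.

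An earlier paragraph of section 1 is softer: "it will explore the feasibility of having a member of the clinical care team providing regular feedback".

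On design:

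- Section 3.1: "In selected sites, we will recruit an additional 30 participants into the app through a BYOD approach study". The next sentence is "Participants recruited from these sites will receive feedback on their data from designated members of the clinical team".
- Section 3.5.2.2.4: "Sites choosing to take part in this part of the study, will identify a member of the clinical care team" to review data and send feedback.
- Section 3.7: block randomisation to one of two arms in each study. In the BYOD study these are the retrospective and the retrospective-plus-momentary strategies (sections 3.1 and 3.5.2.2).
- Section 3.6: for the feedback condition "we aim to recruit 30 participants", with no calculation.
- Section 3.8: no analysis names feedback, and none adjusts for site.
- Section 3.9: one start date for BYOD recruitment (January 2017) and one overall end date (31 December 2017), with no separate dates for the feedback women.

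**The concern.** Whether a woman receives feedback appears to be fixed by where she is recruited. A site that volunteers a staff member for weekly review may differ from other sites in staff motivation, clinic population and support for the app, and each of these could move engagement without any feedback. If the 30 women used the app more than the other BYOD participants, the plan gives no means of telling feedback from site.

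This matters because section 6.5 says the work will explore what affects patient engagement and will inform later trials. A site difference read as a feedback effect would carry forward into their design.

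**Working it through.** **1. Objective against design**

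| What an effect claim needs | What the plan provides |
|---|---|
| Feedback allocated at random | Randomisation covers two arms per study; feedback is not one of them (3.7) |
| Sites chosen independently of outcome | Sites choose to take part (3.5.2.2.4) |
| Women without feedback at the same sites | None described; women recruited there receive it (3.1) |
| Concurrent recruitment | Not stated for the 30 (3.9) |
| A named comparison, with site handled | None (3.8) |
| A comparator for clinicians | None: interviews and the Appendix 7 survey go only to the designated supporters, after the study (3.5.2.2.4) |

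Items 15 and 16 of Appendix 4 go only to women receiving feedback, so they too can only be described. App engagement and the shared acceptance items are the outcomes on which a contrast with other women is possible at all.

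**2. The plan's own figure**

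Section 3.6 gives 96 per arm at 95% confidence and an interval of 10. Reading this as ±10 points and assuming a 50% rate (the plan states none):

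n = 1.96² × 0.5 × 0.5 / 0.10² = 96.04 per arm, about 192 in total. Both stated figures are reproduced. The 30 cannot be, as no derivation is given.

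**3. Precision with 30 women**

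1.96 × √(0.25/30) = 0.179, or about ±18 points, against ±10 in each main arm. For a difference between 30 and 200 women, 1.96 × √(0.25/30 + 0.25/200) = 0.192, or about ±19 points. These are sampling errors for a proportion. They do not measure the confounding, and they do not describe outcomes such as time spent in the app.

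**4. What a site difference alone could do (illustration)**

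The plan gives no site-level rates, so the differences here are assumptions. Take 30 women at 50%, 200 women at 50% + d, no feedback effect, and a two-sided 5% test:

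P(reject) ≈ Φ[(d − 1.96 × SE₀) / SE₁], with SE₀ pooled and SE₁ unpooled.

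- d = 0.10: SE₀ = 0.0964, SE₁ = 0.0976; (0.10 − 0.189)/0.0976 = −0.91, giving about 18%.
- d = 0.20: SE₀ = 0.0918, SE₁ = 0.0969; (0.20 − 0.180)/0.0969 = 0.21, giving about 58%.

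Ordinary between-site variation has a similar influence even without self-selection. Inflate each variance by 1 + (m − 1) × ICC, where m is women per site. With 30 women from 1 to 3 sites and 200 from 5 to 10 sites (all assumed), a nominal 5% test has a true error of about 6–9% at ICC 0.01, 11–22% at 0.05 and 17–33% at 0.10.

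**5. Would a same-site control rescue the effect question?**

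At 80% power, two-sided 5% and a 50% base rate, 30 against 30 detects about 34 points. Splitting the 30 into 15 and 15 detects about 44 points. Numbers of this order support description only.

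**The case against.** The best defence is that this is a feasibility study and the feedback part is exploratory. Section 1 frames it that way, the primary objective in section 2.2.1 is feasibility, section 2.2.3 states no hypothesis about feedback, and the methods for this part are mostly descriptive: interviews, a supporter survey and extra survey items for recipients. That stands, and it limits the harm. It does not answer the point, because the formal objective and the aim still ask about influence, and nothing in section 3.8 bars that inference.

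Four stronger readings are tempting, and the documents do not support them.

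- A reader might infer that feedback is confounded with calendar time as a fact. Section 3.9 gives a single BYOD recruitment window and does not stagger the 30, so this is only possible.
- A reader might infer that the other BYOD women come mostly from other sites. The plan does not say which sites supply them. What can be said is that no same-site comparator is described.
- A reader might infer that a test of 30 against 200 women is planned. Section 3.8 names none. Some comparisons there refer generally to experimental groups, and section 3.5.2.2.4 calls feedback an experimental condition, but section 3.7 counts only two groups.
- A reader might infer that the 30 must be left out of the comparison of monitoring strategies. Section 3.1 recruits them into the BYOD study, and section 3.5.2.2 randomises its participants. If the 30 are randomised too, they can stay in with feedback accounted for.

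**Conclusion.** The point holds as a mismatch between an objective worded as an effect and a design that can only describe. Feedback is unrandomised, sites opt in, and no same-site group without feedback is described, so an effect of feedback cannot be separated from site. Calendar time is a possible further confounder because concurrency is unstated. For clinicians there is no comparison at all.

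The size of the confounding cannot be derived from the documents. The ±18 points is sampling error for a proportion at an assumed 50%. The 18% and 58% rejection rates rest on assumed site differences of 10 and 20 points and on a test that the plan does not specify. The conclusion needs none of these figures; it follows from how feedback is assigned. The reach is one secondary objective and its matching aim, not the randomised comparison of monitoring strategies.

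**What to change.** - Reword the objective in section 2.2.2 and the aim in section 2.2, and the impact wording at the end of section 1, to match the feasibility framing earlier in section 1. The task becomes to describe engagement, acceptance and perceived usefulness among the 30 women and their supporters, with 95% confidence intervals (about ±18 points for a proportion in the women, assuming 50%).
- State in section 3.8 that any contrast with the other BYOD participants is descriptive and that no effect of feedback will be inferred, because sites opt in and there is no same-site comparison group.
- State whether the 30 are randomised between monitoring strategies. If they are, stratify or adjust for feedback in the retrospective versus retrospective-plus-momentary comparison. If they are not, leave them out of it.

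The cost is a narrower claim and a few sentences. Recruitment does not change. Randomising feedback within the opting-in sites would remove the confounding, but with detectable differences of about 34 to 44 points it would not make the effect question answerable at this size.

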### 3.2. Participant recruitment

We will recruit pregnant women attending antenatal clinics in general practices, midwifery services or secondary care NHS centres. Participant recruitment will be conducted by members of the clinical care team who also have a research role, or by Clinical Studies Officers (CSO) who have an honorary contract with or a Letter of Access from the participating NHS centre. Participants will be assessed against our inclusion and exclusion criteria (Table 3) by a member of the clinical care team through a review of medical notes, by the CSO through discussion with the clinical care team, or by asking potential participants directly. Potential participants will be approached opportunistically in the waiting area of participating centres and asked about participation in both studies. If potential participants choose to take part in the study evaluating the tablet computers in antenatal clinics, they will be provided with a copy of the patient information sheet [*Antenatal Mental Health Screening programme – Patient Information Sheet, Version 1.1, dated 06 July 2015*]. If potential participants choose to take part in the study evaluating an app through a BYOD approach, they will be provided with a copy of the patient information sheet [*mHealth for the EMA of mood during pregnancy – Patient Information Sheet, Version 1.2, dated 19 January 2017*]. Participants will be made aware that they can ask any questions about either study, and that they have at least 24 hours before deciding on participation. However, if participants wish to take part in the study on the same day they were approached by a member of the clinical team or a CSO, they will have the opportunity to be consented immediately. In addition, we will explain to participants that refusal to take part in any of these studies or withdrawing from them will not have an impact on their legal rights, medical care or their relationship with those providing medical care. Written informed consent will be taken from those participants who, after receiving all the relevant study information and asking study-related questions, still express their willingness to take part in either study (provided that they meet our participant inclusion and exclusion criteria). Participants can choose to take part in either study (tablet computers in antenatal clinical or app through a BYOD approach), or in both of them.

### 3.2.1. Participant inclusion and exclusion criteria

We followed the recommendations made by Thombs and Ziegelstein (2014) to inform our participant inclusion and exclusion criteria (see Table 3). For these feasibility studies, we will exclude individuals who are not comfortable reading and writing in English, as the EPDS would need to be re-validated for use in any language other than English to ensure that their psychometric properties remain unchanged.

In addition to the criteria listed in *Table 3*, participants will only be eligible to take part in the study evaluating an app through a BYOD approach if they are in their first trimester of pregnancy and if they own an Apple or Android mobile phone.

*Table 3. Participant inclusion and exclusion criteria.*

Inclusion Criteria	Exclusion Criteria
18 years old or older	Diagnosis of any common mental health disorder (i.e., depression or anxiety disorders) as specified in the Diagnostic and Statistical Manual of Mental Disorders, 4 th Edition, Text Revision
Attending antenatal clinics in participating GP practices	Receiving treatment for any common mental health disorder
	Recent personal history of any common mental health disorder (i.e., within the past 12 months)
	Not comfortable reading and writing in English

### 3.3. Measurements

After obtaining written informed consent, we will ask participants to complete a brief survey questionnaire asking for personal (not identifiable) demographic information (Appendix 1). This applies to both studies. For participants in the study using tablet computers in antenatal clinics, we will then conduct a single administration of the Whooley questions, followed by a single administration of the EPDS.

Participants in the study using an app through a BYOD device approach, will be asked to complete the EPDS and, depending on the experimental condition, EMA assessments of mood, sleep, energy, enjoyment and worry for 6 months using their own mobile phones. After 6 months, we will ask them to complete a post-study acceptance survey.

#### 3.3.1. Endpoints

##### 3.3.1.1. *Tablet computers in antenatal clinics*

###### 3.3.1.1.1. Positive predictive value of the Whooley questions

Overall, we will calculate the number of pregnant women who answered *Yes* to any of the Whooley questions AND who scored 10 points or higher on the EPDS, as a proportion of the total number of pregnant women who answered *Yes* to any of the Whooley questions regardless of their EPDS scores.

